2.3.2. Benefit assessment

Symptoms directed physical examinations and clinical assessments that the participants will undergo during the study, will be made by trained clinical staff and can provide participants with valuable knowledge about their health (e.g., in case the study investigator discovers a medical condition unrelated to study treatment, the participant may be referred to the local healthcare system). By receiving HZ/su OR Flu D-QIV in this study, the participants are likely to be protected against HZ or influenza, respectively.

2.3.3. Overall benefit/risk conclusion

Considering the measures taken to minimize risk to participants participating in this study, the potential or recognized risks identified in association with the study vaccines and study procedures are justified by the potential benefits that may be afforded to the participants receiving these vaccines and by the value of the information to be gained.

3. OBJECTIVES AND ENDPOINTS

Table 7 Study objectives and endpoints

Objectives	Endpoints*
Primary	

 To demonstrate the non-inferiority** of humoral immunogenicity of 2 doses of HZ/su when the first dose of HZ/su is co-administered with the mRNA-1273 booster dose compared to HZ/su administered alone. 	
 Anti-glycoprotein E (gE) antibody concentrations expressed as group geometric mean concentration (GMC) ratio at 1 month post-dose 2 of HZ/su (at Week 14 for HZ/suSeq, at Week 12 for HZ/suCoAd).

 To demonstrate non-inferiority** of humoral immunogenicity of 1 dose of mRNA-1273 booster when the first dose of HZ/su is co-administered with the mRNA-1273 booster dose compared to mRNA-1273 booster dose administered alone. 	
 Anti-S Protein antibody concentrations expressed as group GMC ratio§ at 1 month post mRNA-1273 booster dose (at Week 4 for HZ/suSeq and HZ/suCoAd).

 To demonstrate non-inferiority** of humoral immunogenicity of 1 dose of Flu D-QIV when co-administered with mRNA-1273 booster dose compared to Flu D-QIV administered alone based on geometric mean titer (GMT) of Flu D-QIV antibody titers against the 4 influenza strains. 	
 Anti-hemagglutinin inhibition (HI) antibody titers expressed as group GMT ratio against the 4 influenza strains included in Flu D-QIV at 1 month post Flu D-QIV (at Week 6 for FluD-QIVSeq, at Week 4 for FluD-QIVCoAd).

 To demonstrate non-inferiority** of humoral immunogenicity of 1 dose of mRNA-1273 booster when co-administered with Flu D-QIV compared to mRNA-1273 booster dose administered alone. 	
 Anti-S Protein antibody concentrations expressed as group GMC ratio§ at 1 month post mRNA-1273 booster dose (at Week 4 for FluD-QIVSeq and FluD-QIVCoAd).

Objectives	Endpoints*
Secondary	

 To demonstrate the non-inferiority** of humoral immunogenicity of 1 dose of Flu D-QIV vaccine when co-administered with mRNA-1273 booster dose compared to Flu D-QIV administered alone based on seroconversion rate (SCR) difference of Flu D-QIV HI antibody titers against 4 influenza strains. 	
 Anti-HI antibody SCR difference against the 4 influenza strains at 1 month post Flu D-QIV (at Week 6 for FluD-QIVSeq, at Week 4 for FluD-QIVCoAd).

 To characterize the anti-gE humoral immunogenicity at pre-vaccination and at 1 month post-dose 2 of HZ/su. 	
 Seropositivity rate with exact 95% CI at pre-vaccination (at Day 1 for HZ/suCoAd, at Week 2 for HZ/suSeq) and at 1 month post-dose 2 of HZ/su (at Week 14 for HZ/suSeq, at Week 12 for HZ/suCoAd). Anti-gE antibody concentrations expressed as GMC with 95% CI at pre-vaccination (at Day 1 for HZ/suCoAd, at Week 2 for HZ/suSeq) and at 1 month post-dose 2 of HZ/su (at Week 14 for HZ/suSeq, at Week 12 for HZ/suCoAd). Vaccine response rate (VRR) with exact 95% CIs at 1 month post-dose 2 of HZ/su (at Week 14 for HZ/suSeq, at Week 12 for HZ/suCoAd). Mean geometric increase (MGI) from pre-vaccination with 95% CI at 1 month post-dose 2 of HZ/su (at Week 14 for HZ/suSeq, at Week 12 for HZ/suCoAd).

 To characterize the humoral immunogenicity of mRNA-1273 booster dose. 	
 Anti-S Protein antibody concentrations expressed as GMC§ with 95% CI at pre-vaccination (Day 1) and 1 month post mRNA-1273 booster dose (at Week 4 for all groups). MGI§ from pre-vaccination with 95% CI at 1 month post mRNA-1273 booster dose (at Week 4 for all groups).

 To evaluate the humoral immunogenicity of Flu D-QIV. The assessment of SPR and SCR will be based on Center for Biologics Evaluation and Research's (CBER) criteria***. 	
 Anti-HI antibody titers against the 4 influenza strains included in Flu D-QIV expressed as GMTs with 95% CI at pre-vaccination and at 1 month post Flu D-QIV (at Week 6 for FluD-QIVSeq, at Week 4 for FluD-QIVCoAd). Seroprotection rate (SPR) with exact 95% CI at pre-vaccination and at 1 month post Flu D-QIV (at Week 6 for FluD-QIVSeq, at Week 4 for FluD-QIVCoAd), overall and by age category (18-64 and ≥65 YOA). Seropositivity rate with exact 95% CI at pre-vaccination and at 1 month post Flu D-QIV (at Week 6 for FluD-QIVSeq, at Week 4 for FluD-QIVCoAd). MGI with 95% CI from pre-vaccination at 1 month post Flu D-QIV (at Week 6 for FluD-QIVSeq, at Week 4 for FluD-QIVCoAd). SCR with exact 95% CI from pre-vaccination at 1 month post Flu D-QIV (at Week 6 for FluD-QIVSeq, at Week 4 for FluD-QIVCoAd), overall and by age category (18-64 and ≥65 YOA).

Objectives	Endpoints*

 To evaluate the safety and reactogenicity following administration of HZ/su, Flu D-QIV and mRNA-1273 booster dose, up to 30 days post-last vaccination and during the whole post-vaccination follow-up period. 	
 Solicited adverse events (AEs): Number and percentage of participants reporting each solicited local AE and each solicited systemic AE within 7 days (Days 1-7) after each dose and overall. Unsolicited AEs: 
 Number and percentage of participants reporting unsolicited AEs within 14 days (Days 1-14) after each vaccination visit and overall after any vaccination visit for all groups. Number and percentage of participants reporting unsolicited AEs within 30 days (Days 1-30) after each vaccination visit and overall after any vaccination visit for all groups. Serious adverse events (SAEs): 
 Number and percentage of participants reporting SAEs from first dose up to 30 days post-last dose within each group. Number and percentage of participants reporting SAEs from first dose to study end. Potential immune mediated diseases (pIMDs) in HZ/su and mRNA-1273 booster cohort only: 
 Number and percentage of participants reporting of pIMDs from first dose up to 30 days post-last dose within each group. Number and percentage of participants reporting pIMDs from first dose to study end. Adverse events of special interest (AESIs): 
 Number and percentage of participants reporting AESIs from first dose up to 30 days post-last dose within each group. Number and percentage of participants reporting AESIs from first dose to study end. Suspected HZ episodes in HZ/su and mRNA-1273 booster cohort only: Number and percentage of participants reporting clinically suspected HZ episodes from first dose to study end. COVID-19 cases^A: Number and percentage of participants meeting case definitions of COVID-19 from first dose to study end.
Exploratory	

 To evaluate the incidence of lab-confirmed HZ episodes following administration of HZ/su during the whole follow-up period. 	
 Confirmed HZ cases in HZ/su and mRNA-1273 booster cohort only: Number and percentage of participants with polymerase chain reaction (PCR) confirmed HZ episodes from first vaccination to study end.

 To characterize the anti-gE humoral immunogenicity at 1 month post-dose 1 of HZ/su. 	
 Seropositivity rate with exact 95% CI at 1 month post-dose 1 of HZ/su (at Week 6 for HZ/suSeq, at Week 4 for HZ/suCoAd).

Objectives	Endpoints*
	
 Anti-gE antibody concentrations expressed as GMC with 95% CI at 1 month post-dose 1 of HZ/su (at Week 6 for HZ/suSeq, at Week 4 for HZ/suCoAd). VRR with exact 95% CIs at 1 month post-dose 1 of HZ/su (at Week 6 for HZ/suSeq, at Week 4 for HZ/suCoAd). Mean geometric increase (MGI) from pre-vaccination with 95% CI at 1 month post-dose 1 of HZ/su (at Week 6 for HZ/suSeq, at Week 4 for HZ/suCoAd).

 To further evaluate the immune response to the mRNA-1273 booster vaccine via neutralizing antibody titers in a sub-cohort of participants in all study groups. To evaluate further SARS-CoV-2/mRNA-1273 immune responses during the study. 	
 GMT with 95% CIs of SARS-CoV-2 neutralizing antibody titers in a sub-cohort of participants in each study group at pre-vaccination and at 1 month post mRNA-1273 booster dose (Week 4 for all groups). GMCs with 95% CI of anti-receptor binding domain (RBD) protein antibodies at pre-vaccination and 1 month post mRNA-1273 booster dose (at Week 4 for all groups). Anti-nucleocapsid (N) protein seroconversion rate with exact 95% CI from pre-vaccination to 1 month post mRNA-1273 booster dose (at Week 4 for all groups).

[§]Pending final assay evaluations and validations prior to study specimen testing, this primary endpoint for all participants may be replaced with SARS-CoV-2 neutralizing antibody titers, and where applicable derived GMTs, GMT ratios, and MGI.

^{*}The definitions and derivations of endpoint parameters are presented in Section 9.4.

^{**}The success criteria for primary objectives and secondary objectives are presented in Section 9.1.

^{***}CBER criteria are presented in Section 9.3.5.2.3

[#] It should be noted that participants in the HZ/suSeq and FluD-QIVSeq groups will receive their HZ/su or Flu D-QIV, respectively, at Day 14 post mRNA booster vaccine dose at Day 1.

[△] Case Definitions in section 10.2.7

Details related to attributes of endpoint covering intercurrent events, population and treatment definition are provided in Section 9.

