4. STUDY DESIGN

4.1. Overall design

[figure not shown]
This study is a Phase III, randomized, open-label, controlled, multicenter US-based study to evaluate the immune response and safety of both HZ/su in healthy adults 50 YOA and older and Flu D-QIV in healthy adults 18 YOA and older when administered sequentially or co-administered with mRNA-1273 booster vaccination.

The study will be conducted in the U.S. and will enroll participants in 2 main study cohorts, HZ/su with mRNA-1273 booster vaccine administered sequentially or concomitantly and Flu D-QIV with mRNA-1273 booster vaccine administered sequentially or concomitantly, hereafter entitled HZ/su and mRNA-1273 booster cohort and Flu D-QIV and mRNA-1273 booster cohort, respectively ([Figure 1](#)).

Potential participants will be triaged initially to either study cohort (HZ/su and mRNA-1273 booster, Flu D-QIV and mRNA-1273 booster) based upon criteria such as seasonal influenza vaccine availability, known eligibility criteria (such as age and vaccination history), and current study enrollment status. Subsequently, enrolled (i.e., having signed an informed consent form) and eligible participants in each cohort will be randomized in a 1:1 ratio to each of the 2 study groups within each cohort ([Table 8](#)). Staggered randomization will be implemented at the beginning of the study for safety monitoring (see Section [8.2.2.1](#)).

- In the HZ/su and mRNA-1273 booster cohort, 546 participants will be randomized in a 1:1 ratio so that 273 participants are assigned to each study group. The first group (**HZ/suSeq group**) will receive the mRNA-1273 booster dose followed approximately 2 weeks later by the first dose of HZ/su, while the second group (**HZ/suCoAd group**) will receive the mRNA-1273 booster dose co-administered with the first dose of HZ/su. All participants in the HZ/suSeq group and the HZ/suCoAd group will receive the second dose of HZ/su approximately 2 months after the first HZ/su dose. Randomization into each group will be stratified by age (50 to 59, 60 to 69, and \geq 70 YOA) and will be set to ensure a minimum number of 138 participants are assigned to the \geq 70 YOA stratum, 69 participants to each group.

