- In the Flu D-QIV and mRNA-1273 booster cohort, 1000 participants will be randomized in a 1:1 ratio so that 500 participants are assigned to each study group. The first group (**FluD-QIVSeq group**) will receive the mRNA-1273 booster dose followed approximately 2 weeks later by the Flu D-QIV dose, while the second group (**FluD-QIVCoAd group**) will receive the mRNA-1273 booster dose co-administered with the Flu D-QIV dose. Randomization into each group will be stratified by age (18 to 64 and \geq 65 YOA) and will be set to **target (Amended 21 September 2021)** a minimum number of 150 participants are assigned to the \geq 65 YOA stratum, 75 participants to each group.

All study participants will be followed for safety until 6 months post the last dose of the study vaccine with the total duration of study participation approximately 34 and 26 weeks in the HZ/su and mRNA-1273 booster cohort and Flu D-QIV and mRNA-1273 booster cohort, respectively.

Figure 1 Study design overview

EOS = end of study, telephone contact at 24 weeks post last vaccine dose; N = number of participants enrolled and randomized; PLD = post last dose

*Safety Review Team evaluation of 7 days post-dosing after Visit 1 safety data for initial 10% vaccinated in the HZ/suCoAd group and 5% vaccinated in the FluD-QIVCoAd group prior to full randomization in the respective cohorts
(Amended 21 September 2021)

Table 8 Study groups, intervention, and blinding

Cohort	Study Groups	Number of Randomized Participants	Age	Study Interventions	Blinding
					Visit 1 → Phone Contact 2 (Open-label)*
HZ/su and mRNA1273 Booster	HZ/suSeq	273	≥ 50 years**	mRNA-1273 booster HZ/su	x
	HZ/suCoAd	273			
Flu D-QIV and mRNA-1273 Booster	FluD-QIVSeq	500	≥ 18 years**	mRNA-1273 booster Flu D-QIV	x
	FluD-QIVCoAd	500			

*This is an open-label study; however, the specific participant vaccination schedule (sequential or coadministration) will be randomly assigned within each cohort.

** Randomization will be set to ensure at least 69 participants per group will be ≥ 70 YOA in the HZ/su and mRNA-1273 booster cohort and **to target** at least 75 participants ≥ 65 YOA **per group** in the Flu D-QIV and mRNA-1273 booster cohort. *(Amended 21 September 2021)*

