4.2. Scientific rationale for study design

The study was designed after careful considerations of the current healthcare needs and expectations related to vaccinations of the adult population in the U.S.

The U.S Centers for Disease Control and Prevention (CDC) recommends receipt of *Shingrix* to everyone 50 YOA and older, to prevent shingles and its complications [CDC, 2019].

According to CDC, everyone 6 months of age and older should receive a seasonal influenza vaccine every season with rare exceptions. For 2021-2022, CDC recommends use of any licensed, influenza vaccine that is appropriate for the recipient's age and health status, including inactivated influenza vaccine, recombinant influenza vaccine, or live attenuated nasal spray influenza vaccine [[CDC](#), 2021a].

As of summer, 2021, vaccines against COVID-19 in people ages 12 years and older have become an essential part of healthcare procedures to control the COVID-19 pandemic.

With the emergence and spread of the SARS-CoV-2 virus variants that may not be sufficiently controlled by the primary vaccinations, periodic administration of booster COVID-19 vaccines after primary vaccination is either already recommended for specific populations or is under consideration by various health agencies. (Amended 21 September 2021)

Current CDC guidance on the coadministration of COVID-19 vaccines with other routine vaccinations is as follows: "COVID-19 vaccines and other vaccines may now be administered without regard to timing. This includes simultaneous administration of COVID-19 vaccine and other vaccines on the same day, as well as coadministration within 14 days. It is unknown whether reactogenicity of COVID-19 vaccine is increased with coadministration, including with other vaccines known to be more reactogenic, such as adjuvanted vaccines or live vaccines" [[CDC](#), 2021c].

The current study is designed to provide reactogenicity, safety, and immunogenicity data for when a seasonal influenza virus vaccine or an adjuvanted Herpes Zoster subunit vaccine is administered at the same time or two weeks following a potential COVID-19 mRNA booster vaccine. This is important needed data expected to help public health authorities provide more evidence-based guidance and health care providers to make decisions on such vaccine coadministrations.

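### The primary objectives claim non-inferiority to each vaccine administered alone, but the only control is sequential vaccination, so the result supports only co-administered versus sequential; the gap matters most for anti-S

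*Protocol*

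**What the plan says.** Protocol Table 7, repeated in SAP 2.1, frames both anti-S objectives (Hypotheses 2 and 4) as non-inferiority "compared to mRNA-1273 booster dose administered alone", with anti-S measured at Week 4 in all groups. The anti-gE and HI primary objectives, and the secondary seroconversion-rate (SCR) objective tested as Hypothesis 5, use the same form: HZ/su or Flu D-QIV given alone.

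Protocol 4.1 defines the controls differently. The HZ/suSeq group "will receive the mRNA-1273 booster dose followed approximately 2 weeks later by the first dose of HZ/su". The FluD-QIVSeq group gets the booster "followed approximately 2 weeks later by the Flu D-QIV dose". A note under Table 7 says that participants in the sequential groups "will receive their HZ/su or Flu D-QIV, respectively, at Day 14 post mRNA booster vaccine dose at Day 1". SAP 2.1 does not carry that note. Protocol 4.2 describes the design as studying a second vaccine that "is administered at the same time or two weeks following a potential COVID-19 mRNA booster vaccine".

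The hypotheses and success criteria (Protocol 9.1, SAP 8.1) are written as Seq versus CoAd, and the power tables are labelled sequential versus co-administered.

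**The concern.** The objective names one comparator and the trial supplies another. The success rule connects them: Protocol 9.1 and SAP 8.1 count the objective as met when the upper 95% limit of the Seq/CoAd ratio is below 1.5. A result about same-day versus staggered vaccination would then be filed under an objective about a lone booster.

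The two contrasts coincide only if HZ/su or Flu D-QIV given at Week 2 leaves Week 4 anti-S unchanged. Neither document argues this. If the second vaccine lowers anti-S, the control mean falls and the effective margin against a lone booster is wider than 1.5. If it raises anti-S, the effective margin is tighter.

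For anti-gE and HI, *alone* is also inexact, because those controls are vaccinated about two weeks after the booster. The argument is weaker there: nothing is scheduled between the control vaccine and its endpoint sample except the second HZ/su dose, which belongs to the regimen.

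**Working it through.** **1. Can a booster-only Week 4 value be obtained?**

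- Protocol Table 8 has four groups, and none receives only the booster.
- Protocol Tables 4 and 5 place Visit 2 (second vaccine) at 14-21 days and Visit 3 (anti-S sample) at 25-35 days after the booster. The second vaccine therefore precedes the sample by 25 - 21 = 4 to 35 - 14 = 21 days.
- Protocol Table 12 tests anti-S only at Day 1 and Week 4. The Week 2 sample in the sequential groups, drawn before the second vaccine, is assigned to anti-gE or HI. The co-administration groups have no Week 2 draw (Protocol Table 2).

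So the planned samples cannot recover a Week 4 contrast against a lone booster.

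**2. Does the order hold for every per-protocol participant?**

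SAP Table 8 keeps HZ/suSeq participants in the per-protocol set with Visit 2 at 13-49 days and Visit 3 at 25-49 days. SAP Table 9 uses 13-42 and 21-42 days for FluD-QIVSeq. These ranges overlap, and neither table sets a minimum interval from Visit 2 to Visit 3. The second vaccine comes before the sample as scheduled, but the analysis limits do not guarantee it, and the gap between vaccines can be well beyond two weeks.

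**3. Reproduce the stated anti-S powers (Protocol Tables 18 and 19).**

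Inputs: SD 0.45 on log10, margin 1.5, assumed Seq/CoAd ratio 1.1, one-sided alpha 0.025, n = 245 (HZ) or 450 (Flu) per group.

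- Distance to the margin: log10(1.5) - log10(1.1) = 0.1761 - 0.0414 = 0.1347.
- SE = 0.45 × √(2/n) = 0.04066 (n = 245) or 0.03000 (n = 450).
- Distance/SE = 3.31 or 4.49. The noncentral t gives 91.1% and 99.4%, as stated.

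**4. Size of the mismatch under an assumed effect.**

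Let f be the anti-S GMC in the sequential group divided by the GMC after a truly lone booster. The documents give no f. Then Seq/CoAd = f × alone/CoAd, and the effective margin against *alone* is 1.5/f. If the true alone/CoAd ratio is exactly 1.5, the distance to the margin is log10(1.5) - log10(1.5f) = -log10(f). The chance of declaring non-inferiority is Φ(-log10(f)/SE - 1.96). The noncentral t agrees to within 0.1 percentage point.

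| Assumed f | Effective margin vs alone | -log10(f) | HZ, n = 245 | Flu, n = 450 |
|---|---|---|---|---|
| 1.05 | 1.43 | -0.0212 | 0.7% | 0.4% |
| 1.00 | 1.50 | 0 | 2.5% | 2.5% |
| 0.95 | 1.58 | 0.0223 | 7.9% | 11% |
| 0.90 | 1.67 | 0.0458 | 20% | 33% |

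Example, HZ at f = 0.95: 0.0223/0.04066 = 0.548; Φ(0.548 - 1.960) = 7.9%.

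**The case against.** The strongest reply is that every operative part of the plan already states the right contrast. The hypotheses, success criteria and power tables all say Seq versus CoAd, the rationale in Protocol 4.2 describes staggered dosing, and the note under Table 7 discloses it. No margin, alpha, sample size or decision rule depends on the word *alone*, which might mean only that no other vaccine is given at that visit. The documents contain no written conclusion against a lone booster, so an overclaim is foreseen rather than found. The interim safety analysis is done (SAP 11), so amending the protocol for wording would come late.

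Most of this stands, and it confines the point to how the objective is stated and what may be concluded. It does not remove the point. Neither document defines *alone* as a separate visit, the note under Table 7 does not redefine it, and the success rule still declares met an objective that says *alone*.

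A reader might infer that the anti-S tests are anti-conservative, or that their type I error is inflated to 8-33%. The documents do not support that. They give neither sign nor size for any effect of the second vaccine on anti-S. The larger figures above rest on an assumed reduction and on a true alone/CoAd ratio of exactly 1.5, and they are error rates for a hypothesis the plan does not formally test.

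**Conclusion.** The objectives overstate the comparator and should be reworded. Meeting the criterion for Hypothesis 2 or 4 supports co-administered versus sequential administration, and no claim against the booster alone. The Seq-versus-CoAd tests are valid, with 2.5% one-sided type I error and the stated powers.

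Bias relative to *alone* is unknown in direction and size. Across an assumed change in control-arm anti-S from +5% to -10%, the chance of declaring non-inferiority at a true alone/CoAd ratio of 1.5 runs from 0.7% to 20% (HZ) and from 0.4% to 33% (Flu). This range illustrates sensitivity and does not estimate bias.

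The case is strongest for anti-S. For anti-gE, HI and SCR the wording is inexact for the same reason, but no size was worked out. A reader might also infer that every control participant has had both vaccines by the anti-S sample. That holds under the protocol windows, but SAP Tables 8 and 9 do not guarantee it.

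**What to change.** - In SAP 2.1 and 2.2 and in the report, and in Protocol Table 7 if the protocol is amended for another reason, replace *administered alone* with: administered sequentially (booster first, HZ/su or Flu D-QIV at a later visit, planned Week 2). Apply this to the four primary objectives and to the secondary SCR objective (Hypothesis 5), so that the set stays consistent.
- In SAP 8.1 and 8.2, state that the conclusions concern co-administered versus sequential administration and that no claim against the booster alone will be made. In the same edit, correct the labels in SAP 8.1.1 and 8.1.2 that describe the anti-S models as addressing the HZ/su or Flu D-QIV response.
- Report, for the sequential groups in each per-protocol set, the distribution of the actual interval between vaccines and of the interval from second vaccine to anti-S sample, with the number sampled at or before the second vaccine.

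Cost: wording, one descriptive table and a slightly narrower claim. Visits, vaccinations, sample size, power and hypothesis tests are unchanged.
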